Project summary (objective, intervention, participants, results) :	
The general objective of the integrated and multisectoral services package (PASIM) is to reduce the incidence and prevalence of wasting through integrated interventions, including, among other things, strengthening the activity of community care groups. The members of the care groups make home visits to children aged 6-23 months (or up to 59 months when the children are under treatment for wasting or have been discharged in the previous 6 months) to deliver messages for behavioral change related to complementary feeding, health and hygiene ; deliver nutritional supplement and water purification inputs; improve screening coverage (training and supervision of families to take the Mid-Upper Arm Circumference measurements, referral of malnourished cases); and verify adherence to treatment of malnourished cases, in the health district of Mongo, Guéra province, Chad, Central Africa.
 
The evaluation of the impact of PASIM will be based on a cluster randomized controlled trial, consisting of 100 villages or clusters of villages. The selected evaluation model will be that of a comparison of control groups (n=50; no implementation of the intervention) and intervention (n=50) through the follow-up of 3 cohorts :
 
1- Longitudinal in-home follow-up of a semi-open cohort of 1,750 children aged 6 months at enrollment (included continuously for 7 months and all followed through to the end of the study, which will last 9 months in total).2- Longitudinal follow-up of all children aged 6-23 months enrolled for wasting treatment, based on health system records.3- Longitudinal follow-up at home for 6 months of a closed


cohort of 700 children aged 6-23 months at inclusion, discharged from a treatment for acute malnutrition.
 
The primary impact results are as follows:
 
 - The longitudinal prevalence of wasting at the end of the study (Cohort 1). - The recovery rate (Cohort 2). - The incidence of relapse during the 9 months of the intervention (Cohort 3). 
Secondary impact results include, but are not limited to :
 
 - The incidence of wasting during the 9 months of the intervention (Cohort 1) ; - The screening coverage (cohorts 1 and 3); - The proportion of wasting cases enrolled in a treatment program (cohorts 1 and 3); - The adherence to treatment (cohort 2) during the 9 months of the intervention. 	
Study Tools :	Questionnaires, anthropometric measurements, and biological measurements on capillary blood by finger puncture (rapid malaria test, hemoglobin level)
Consent Forms :	See Appendix 1
Instruments :	See Appendix 2
Duration of the project :	9 months (April 2021 - December 2021)
Sponsor :	Foreign, Commonwealth & Development Office (FCDO) via the United Nations Children's Fund (UNICEF)
Agency of setting implementation :	Sahelian Alliance for Applied Research for Sustainable Development (ASRADD)
Partner institution :	Ministry of Public Health (DNTA)
Developer :	International Food Policy Research Institute (IFPRI)
Data collection :	Moustagbal
Project Contacts :	[name] (PI) - IFPRI Senegal - [contact] [name] (PI) - IFPRI USA - [contact] [name] - IFPRI Senegal - [contact]

Summary

1	PROBLEM STATEMENT AND STUDY RATIONALE	7
2	GENERAL OBJECTIVE	8
3	RESEARCH METHODS	10
3.1	FRAMEWORK OF THE STUDY	10
3.1.1	STUDY AREA.....	10
3.1.2	PCIMA NATIONAL PROGRAM	11
3.2	THE INTERVENTION	13
3.2.1	BENEFICIARIES OF PASIM	13
3.2.2	DELIVERY PLATFORM: COMMUNITY CARE GROUPS.....	13
3.2.3	PASIM SERVICES.....	13
3.3	TARGET POPULATION AND STUDY POPULATION	15
3.4	RESEARCH QUESTIONS	16
3.5	IMPACT STUDY	16
3.5.1	IMPACT STUDY MODEL	16
3.5.2	STRATIFICATION AND RANDOMIZATION	17
3.5.3	SAMPLE SIZE, SAMPLING, APPROACHES, AND INCLUSION CRITERIA.....	18
3.5.4	STUDY RESULTS	22
3.5.5	MEASURES AND PROCEDURES.....	24
3.5.6	DATA ANALYSIS	26
3.6	COST AND COST-EFFECTIVENESS STUDY.....	26
3.7	DATA MANAGEMENT	27
3.8	DISSEMINATION STRATEGY	28
4	ETHICAL CONSIDERATIONS	28
4.1	COMMUNITY INFORMATION	28
4.2	VOLUNTARY AND INFORMED PARTICIPATION	28
4.3	RISKS AND SERIOUS ADVERSE EFFECTS	29

Worldwide, 47 million children under the age of five suffer from wasting¹ (1). Wasting significantly increases the risk of death: it kills 875,000 children under the age of five per year (2). All member states of the World Health Assembly (WHA) have agreed to reduce and maintain the prevalence of wasting to less than 5% by 2025 (3). However, the prevalence of wasting remains persistently high in many West and Central African countries such as Mali (14.8%), Mauritania (13.5%), Chad (12.9%) and Niger (10.1%). Wasting trends suggest that the WHA goal will not be achieved in these countries, despite their commitment to combat wasting as expressed in their nutrition policies (4). Progress in reducing the burden of wasting is hampered by a number of factors. First, programmatic evidence on how to prevent wasting is limited. There is a growing body of evidence on the effectiveness of dietary supplements in preventing wasting, but little is known about the effectiveness of other strategies such as social and behavior change communication (SBCC) (with or without supplements), cash transfers, or water, hygiene, and sanitation (WASH) interventions (5). Second, coverage of community-based management of wasting (CIMCI) treatment remains low in many settings (6). On the supply side, documented constraints include the complexity of current treatment procedures, which disproportionately affects resource-limited settings, and frequent shortages of treatment commodities. On the demand side, low participation in screening and low treatment uptake and adherence are key constraints to effective treatment. The recent PROMIS studies in Mali and Burkina Faso demonstrate that screening uptake can be more than doubled by providing small quantities of lipid-based nutrient supplements (SQ-LNS) combined with social and behavior change communication (SBCC) as incentives for participation (7,8). However, these studies showed that increased screening in these settings did not automatically lead to increased treatment coverage, which remained below 25%.

There is an urgent need to test innovative solutions to prevent wasting and increase screening, treatment initiation and adherence. Options include integrating prevention into screening to increase coverage and prevent wasting; strengthening referral processes for wasted children and supporting and encouraging parents to enroll their children in treatment; establishing outreach screening and treatment units; transferring some responsibility for treatment to community health workers; and/or simplifying treatment procedures for both parents and service providers.

In response to this urgent need, UNICEF and IFPRI started a multi-country partnership to generate evidence on wasting prevention and treatment interventions in four countries: Chad, Mali, Mauritania, and Niger.

In Chad and Mali, impact evaluations will be conducted to generate solid evidence of the effectiveness of integrated interventions to reduce wasting. Impact evaluation in

¹ Defined in children 0-59 months of age as a weight-for-height score of less than -2 z-score according to WHO weight-for-height references (13); depending on the context and the measurement tools used, wasting is also defined by a brachial perimeter of less than 125 mm in a child aged 6-59 months or by the presence of bilateral edema (0-59 months).

these countries will be combined with a cost study and a documentation of the implementation process. In Mauritania and Niger, in-depth implementation research will be conducted to generate the necessary evidence on how integrated nutrition services are implemented in the field. The proposed studies will help fill important knowledge gaps by assessing the operational feasibility, impact and cost-effectiveness of community-based integrated interventions that use simple procedures to integrate all elements of the continuum of care from wasting prevention to treatment, into a single platform at the community level in four West African countries (**Figure 1**). The evidence generated through this partnership will inform national, regional and global policies on wasting and is consistent with the Global Plan of Action on Child² Wasting (9), ³and the WFP-UNICEF regional partnership.

[figure not shown]

Figure 1: Conceptual Framework of Continuum of Care for wasting

2 General objective

The overall objective of *the intervention* is to reduce the longitudinal prevalence of wasting in children aged 6 to 23 months inclusive (corresponding to a peak prevalence) by integrating several approaches along the continuum of care for wasting into *an integrated, multisectoral package of services (PASIM)*.

The main objective of *the research* is to provide strong evidence of the effectiveness of the integrated interventions of the PASIM to reduce wasting.

The implementation of PASIM will be led by the Sahelian Association for Applied Research and Sustainable Development (ASRADD) in collaboration with the health

² In March 2020, the inter-agency Global Action Plan on child wasting (GAP) was published. UNICEF is partnering with WHO to produce evidence to inform both the GAP and the review of WHO normative guidelines. This project will help fill key knowledge gaps related to this collaboration with WHO.

³ Evidence from this partnership between UNICEF and IFPRI will also include other key stakeholders, including WFP. Within the framework of the regional partnership between UNICEF and WFP, and in particular the associated learning agenda, this project will be conducted to help highlight current gaps in integrated approaches to reduce child wasting, from prevention to treatment.

services of the health district of Mongo, Guéra province, and other implementing partners in the zone. The activities will take place at the health center and community levels, and include i) a prevention component combining the strengthening of community care groups (who will conduct home visits to deliver behavior change messages) and the distribution of a nutritional supplement (CSB++) to [6-11] months old children diagnosed as non-wasted (as a result of the green MUAC) and water purification inputs to all [6-11] months old children unconditionally (regardless of wasting status); ii) a component related to strengthening screening and referral that will involve families (family MUAC approach), with [6-23] months old children, trained and supervised by community care groups (who will also conduct routine screening); children diagnosed as wasted will be referred and will receive treatment (including food supplements) at the FARNE or nutritional units; iii) a treatment component that includes strengthening the protocol for integrated management of acute malnutrition (PECIMA) currently in use in Chad, as well as support from community groups through follow-up home visits to wasting cases for counseling and verification of adherence and compliance to treatment; and iv) a final relapse prevention component combining a 6-month home follow-up by community care groups for [6-23] months old children who recovered from wasting to provide nutritional counseling, a preventive nutritional supplement (CSB++), water purification inputs, and a supervision of testing by families.

3 Research Methods

3.1 *Framework of the study*

In 2015, the SLEAC survey conducted in Chad showed that the coverage of SAM care was 37% and was considered moderate (12). The barriers identified by the survey are a strong lack of knowledge about malnutrition and a poor understanding of treatment and the IMCI programs, the barrier of distance and the availability of means to get to health centers.

Analysis of 2018 and 2019 admission data in the outpatient or therapeutic nutritional units of the Guéra shows a high rate of admission of children already known to PECMAS services, specifically children in relapse (after an episode successfully treated) and children readmitted after dropping out of the program (11). This rate decreased significantly between 2018 and 2019, but still exceeds 10% of children admitted in the age groups above 6 months. In addition, exit data show that successful treatment increased significantly between 2018 and 2019, with a significant decrease in the dropout rate from 7.5% to 2.6%. The death rate is quite low, around 0.5%. On the other hand, the occurrence of shortages of RUSF in UNA as reported in the monitoring files (zero stock at the end of the month) over a 2-year period reveals that all the health centers monitored suffered at least one shortage in 2 years. A third of the 18 facilities had shortages observed 5 times or more over the 24 months observed.

3.1.2 PCIMA National Program

Chad's current national protocol for the management of acute malnutrition has been implemented since 2014. It technically describes the organization of the continuum of care for wasting at the central (national), provincial, district, health center and community levels. It describes all aspects of the implementation of screening and treatment. Routine PCIMA services for the treatment of MAM and SAM are available in health centers throughout the country.

The program for the management of severe or moderate acute malnutrition implemented by the Ministry of Health is currently operating in all health centers in Mongo for the ambulatory management of uncomplicated cases (UNS Supplementary Nutritional Units for MAM, UNA Ambulatory Nutritional Units for SAM). In the district hospital, the pediatric services ensure the management of SAM with medical complications (Therapeutic Nutritional Unit, UNT). In some communities, MAMs are also treated in FARNEs (Homes for learning, nutritional rehabilitation and awakening), which are run by the community and NGO actors in partnership with the health services.

a) *Screening platforms*

Passive screening is done during preventive child care and curative consultations or immunization sessions by qualified health workers, doctors, and nurses. Passive screening is included in the outreach strategy (health worker going to the village for consultation), but the health center does not organize active screening (in the form of campaigns, for example). Health staff use either tape measures (MUAC) or weight-for-height measurements for diagnosis. However, following the COVID19 pandemic,

precautionary measures have been taken and screening of children has been limited to measuring MUAC, including in health centers. Routine screening is done in the community by CHWs, care groups and mothers using MUAC.

b) Reference and treatment of MAM and SAM

When community workers screen a child for acute malnutrition, the child is: i) either diagnosed as negative (code green, MUAC ≥ 125 mm); ii) or diagnosed as MAM positive ($115\text{mm} \leq \text{MUAC} < 125\text{mm}$, code yellow); iii) or diagnosed as SAM positive (MUAC $< 115\text{mm}$ or bilateral edema, code red). In the case of SAM, the mother-child couple is referred to the health center for confirmation of the diagnosis based on the MUAC and initiation of treatment. If the diagnosis is confirmed, the child is examined to verify the presence or absence of medical complications. Following the COVID19 pandemic, only the MUAC criterion is currently used to screen children.

In the absence of signs of complication, the MAM child is admitted to an outpatient program (UNS or FARNE) with a scheduled follow-up every two weeks. The duration was extended following the COVID19 pandemic; follow-up is currently monthly. The mother receives a ration of food supplements to be given to the child every day (RUSF or CSB++). In the absence of complications, and after a successful appetite test, the SAM child is included in an outpatient treatment program (UNA) with follow-up scheduled every week. The duration was extended following the COVID19 pandemic; follow-up is currently every two weeks. The mother receives a ration of food supplements (RUSF) to be given to the child every day. Complicated cases of SAM or MAM or cases with edema are referred for inpatient treatment at the hospital which has a pediatric ward (UNT ward).

Children are discharged from these treatment programs if they reach a weight-for-height->-2 z-scores and a MUAC ≥ 125 mm and the absence of bilateral edema for two consecutive visits.

c) Psycho-cognitive stimulation program at UNA/UNT

During the rehabilitation of children under treatment at UNA/UNT, their psycho-cognitive stimulation should begin, and continue after discharge, to reduce the risk of mental and physical sequels. Psychosocial stimulation should be done by the doctor and nurses. The social worker is in charge of organizing the sessions.

This program includes activities such as :

- Organizing sessions to teach mothers how to make toys themselves with cheap and salvageable materials;
- Organizing training sessions to teach mothers the importance of games and discovery in providing the psycho-cognitive and physical stimulation the child needs (this is an integral part of the treatment);

- Keeping the mother with the child and encourage her to feed, carry, comfort, and play with him/her as much as possible.

3.2 *The intervention*

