- Referral to the health center of [6-59] months old children screened as malnourished (result of MUAC orange or red): The VGS refers children who are diagnosed as malnourished to the health center using a referral coupon and makes a note in the care group's follow-up logbook; the ASRADD promoter regularly retrieves this data and follows up with the health center. If the promoter notices that a certain number of children did not follow up on the referral, he returns to the care group, which returns to the families to identify the children who did not go to the health center, understand the reason, and seek solutions with the families.
- Follow-up of [6-59] months old children under treatment and for 6 months after discharge from the national treatment and consolidation program (if eligible): VGS follows children under treatment until they recover (taking treatment until they are cured) and for the whole duration of their consolidation (for children cured of severe emaciation) through home visits.

- They monitor treatment adherence (i.e., families follow the planned schedule of visits and receive inputs for treatment or consolidation) and treatment compliance (i.e., the malnourished or consolidating child receives the planned dose of therapeutic or supplementary food each day).
- They also deliver a water purification input: bleach or flocculant/decontamination sachets for the purification of the water for the entire household.
- Upon recovery or discharge from consolidation program for a child aged [6-23] months, follow-up is extended for 6 months (or until the child is 59 months old) with the delivery of the complete prevention package :
 - Behavior change communication
 - Monthly delivery of a nutritional supplement: enriched flour (CSB++), at a rate of 3 kg/month/child beneficiary
 - Monthly delivery of a water potabilization input: bleach or flocculant/decontamination sachets for the potabilization of the water of the whole household.

Other activities of the care group are carried out upstream of the peak of acute malnutrition (before the child's 6 months of age and during pregnancy) and essentially include activities promoting good practices for the prevention of all forms of malnutrition and illness during the 1,000-day period (which extends from the mother's pregnancy to the child's second birthday), integrating the promotion of good maternal diet and the promotion of exclusive breastfeeding in the first 6 months.

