3.2 Study design

We designed a two-arm, cluster-randomized, non-blinded, longitudinal, effectiveness trial to study the impact of the PASIM intervention as compared to the standard of care in the study area. Two study groups will be formed, a control/comparison group, and an intervention group receiving the integrated package of interventions. The activities of the control and intervention group are summarized in Table 1.

Table 1: intervention package in intervention and comparison groups

	Intervention	Comparison
Prevention	Integrated community care group (CCG) Weekly home visits: BCC (pregnancy to 23 mo) Monthly village-level distribution in presence of CCG volunteer of 360 g of soap + 1 L of bleach + 3 kg of CSB++ (non wasted 6-11 mo) MNPs (12-23 mo)	No intervention (some pre-existing CCG with no support since 2019; some areas with punctual preventive interventions)
Screening	Family MUAC (6-23 mo) Integrated CCG (6-23 mo) Weekly home visits: training and supervision of family MUAC, MUAC screening, referral, follow-up on referral through supervisor (NGO promoter)	No intervention (Contact with existing CCG and health system ; some areas with caregivers trained to family MUAC in 2019)
Treatment	Current CMAM protocol (adapted), health center or community site (6-59 mo) SAM/MAM treatment, MUAC only, reduced intensity, culinary demonstrations at community sites Strengthened RUTF/RUSF supply chain Integrated CCG (6-23 mo) Weekly home visits: general and AM specific counselling, ensure RUSF/RUTF compliance Monthly village-level distribution in presence of CCG volunteer of 360 g of soap + 1 L of bleach (6-23 mo)	Same as for intervention group Strengthened RUTF/RUSF supply chain No intervention
Relapse prevention	Integrated CCG Weekly home visits: specific counselling on IYCF (6-23 mo for 6 mo) Monthly village-level distribution in presence of CCG volunteer of 200 g of soap + 400 mL of bleach + 3 kg of CSB++ (6-23 mo for 6 mo)	No intervention

Abbreviation used: BCC, Behavior Change Communication; CCG, Integrated community care group; CMAM, Community-based management of acute malnutrition; CSB++, improved corn-soy-blend for young children; MAM, Moderate wasting; MNPs, Micronutrients powder; MUAC, Mid-upper arm circumference; RUSF, Ready-to-use supplementary food; RUTF, Ready-to-use therapeutic food; SAM, Severe wasting.

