 - Minimum meal frequency for children, defined as the proportion of children who had eaten the day before the survey: 2 meals for breastfed children 6-8 months, 3 meals for breastfed children 9-23 months, or 4 meals for non-breastfed children 6-23 months.
 - Minimum acceptable diet, defined as the proportion of children with both minimal dietary diversity and minimal meal frequency on the day before the survey.
 - Consumption of iron-rich or iron-fortified foods in children.
- Practices related to water, hygiene and sanitation, as per Standard USAID indicators related to drinking water source, treatment, storage; hand washing; and sanitation
- Vaccination coverage, defined as the proportion of children with complete vaccination for their age.

For Cohort 2⁵:

- Nutritional status (measured by MUAC) at admission in treatment unit.
- The duration of treatment defined as the number of days spent on treatment (between admission and discharge).
- Treatment adherence defined as the proportion of cases enrolled for treatment who received timely treatment from dedicated services until recovery.
- The treatment outcome (drop-out, death, transfer, non-response rates).
- longitudinal prevalence of childhood morbidity defined by the number of days for which signs of these morbidities were reported divided by the total number of days observed/reported in the recall periods.

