5.2 Creation of variables related to treatment (cohort 2)

Recovery from MAM or SAM will be defined as achieving a normal nutritional status (defined as MUAC \geq 125 mm) within 3 months after treatment admission.

We will calculate adherence as per the national protocol, i.e. treatment consultations are attended every 2 weeks for SAM treatment or 4 weeks for MAM treatment.

Version SAP 2.0: We added 2 definitions for adherence. Definition 2) is same as (1), with a tolerance if the missed consultation was not actually organized by the treatment unit; Definition 3) is same as (2), with a tolerance if the missed consultation(s) corresponded to a shortage of RUTF or RUSF.

We will inspect the registers data and correct any data entry mistake when it does not correspond to the national protocol. Specifically:

- All children who missed 2 consecutive scheduled consultations will be recoded as default, and their follow-up visits will be dropped from the dataset entry and recoded as a new entry following re-admission after default. The first consultation after default will be considered as admission consultation.
- Exit type coded as recovery will be recoded to “mistakenly coded as recovery” when exit MUAC is less than 125 mm.
- Other exit types will be recoded to “recovered” when exit MUAC is 125 mm or more.

6 Statistical analysis

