6.4.2 Sub-group analyses

For cohort 1 and 3 data, we will conduct exploratory subgroup analysis of treatment coverage on the sub-group of children with wasting and children recovering from wasting.

For cohort 2 data, we will conduct exploratory subgroup analyses by type of treatment unit, because two distinct treatment protocols are used in Chad for SAM and MAM, and within MAM treatment, implementation strategies are different between the health center platform and the community platform, including the use of two distinct treatment products. These analyses may help explain wasting treatment outcome results.

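### Adherence definition 3 (SAP 5.2) excuses visits missed during a RUTF or RUSF shortage but not a CSB++ shortage, so it is not comparable across types of treatment unit

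*Protocol*

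**What the plan says.** Treatment adherence is a secondary outcome of cohort 2. SAP 3.4.2 defines it as follows: "Treatment adherence defined as the proportion of cases enrolled for treatment who received timely treatment from dedicated services until recovery".

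SAP 5.2 puts it into practice in three ways:

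- Definition 1 follows the national schedule: "treatment consultations are attended every 2 weeks for SAM treatment or 4 weeks for MAM treatment".
- Definition 2 relaxes this "with a tolerance if the missed consultation was not actually organized by the treatment unit".
- Definition 3 goes one step further: "Definition 3) is same as (2), with a tolerance if the missed consultation(s) corresponded to a shortage of RUTF or RUSF".

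Three other places bear on which products matter:

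- Protocol 3.1.2, on MAM children admitted to a UNS or a FARNE: "The mother receives a ration of food supplements to be given to the child every day (RUSF or CSB", where the last product is CSB++.
- SAP 6.4.2, on MAM treatment: "implementation strategies are different between the health center platform and the community platform, including the use of two distinct treatment products". It does not name the two products.
- SAP 3.2, Table 1, treatment row, in both arms: "Strengthened RUTF/RUSF supply chain". CSB++ appears in that table only for prevention and relapse prevention.

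**The concern.** Definition 3 appears meant to keep supply failures from being scored as poor attendance. That purpose fits Protocol 3.2.3, where adherence means that "families follow the planned schedule of visits and receive inputs for treatment or consolidation". A tolerance of this kind has to cover every product the treatment units dispense. If it covers some and not others, the same event is scored differently according to where the child is treated.

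Two uses of the outcome are exposed. SAP 6.4.2 plans exploratory analyses of cohort 2 by type of treatment unit, to help explain the treatment results, and definition 3 would not mean the same thing from one unit type to the next. In the comparison of arms, a difference between arms in where children are treated could appear as a difference in adherence.

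**Working it through.** The plan gives no sample size, power or expected value for adherence, so there is no figure to reproduce. The check sets the passages side by side.

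**Step 1: which products are dispensed for treatment.** Protocol 3.1.2 names two rations for MAM outpatients, RUSF and CSB++. SAP 6.4.2 says the two MAM platforms use two different products. Together these indicate that one platform uses CSB++. This is an inference: neither section says which platform uses which product.

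**Step 2: which shortages are excused.** Definition 3 names RUTF and RUSF. The abbreviation list under SAP Table 1 defines RUSF and CSB++ as separate items, so RUSF cannot safely be read as covering any MAM product.

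**Step 3: how definition 3 scores each case.**

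| Missed consultation | Result under definition 3 |
|---|---|
| Not held by the unit, for any reason, including a CSB++ shortage | Excused (carried over from definition 2) |
| Held, missed during a RUTF or RUSF shortage | Excused |
| Held, missed during a CSB++ shortage | Non-adherent |

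Only the third row is at fault.

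**Step 4: what this does to the arm contrast.** Let p1 and p0 be the shares of children treated at CSB++ sites in the intervention and control arms. Let m be the proportion of children at those sites who are classed as non-adherent solely because of the third row. Adherence is understated by p1 × m in one arm and p0 × m in the other. If m is the same in both arms, the error in the non-adjusted difference (intervention minus control) is −(p1 − p0) × m.

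- The error is zero if the arms use CSB++ sites equally (p1 = p0) or if the third row never occurs (m = 0).
- Its sign depends on p1 − p0.
- Within CSB++ sites alone, an equal m in both arms leaves the arm difference unaffected, although adherence is too low in both.

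The documents give none of p1, p0 or m, so the expression cannot be evaluated.

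**The case against.** The strongest reply is that little depends on this. Definition 3 is one of three definitions, and the other two are untouched. The outcome is secondary, and SAP 3.2 calls the cohort quasi-experimental and asks for caution in reading it. SAP 6.1 lists type of nutrition unit as an adjustment variable for cohort 2, which addresses the main route to arm bias. All of this stands and limits the point. It does not repair the non-adjusted model, which SAP 6.1 says will also be presented, or make definition 3 mean the same thing across unit types.

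It can also be said that the CSB++ platform is inferred and that Table 1 mentions only RUTF and RUSF under treatment. That is fair, but Protocol 3.1.2 lists CSB++ as a MAM ration, and no other second MAM product is named that would fit SAP 6.4.2.

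A reader might infer four stronger things that the documents do not support:

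- **Every visit missed during a CSB++ shortage is penalized.** Not so: if the shortage led the unit to cancel the session, definition 2 excuses it.
- **The bias runs against the intervention.** SAP 3.2 says screening may bring in children with different characteristics. It does not mention a shift toward CSB++ sites and gives no direction.
- **A planned platform comparison is biased.** SAP 6.4.2 plans subgroup analyses by unit type and states no head-to-head contrast of platforms. The harm comes from reading definition 3 across those subgroups.
- **The effect can be sized from the shortage history in Protocol 3.1.1.** Those records concern RUSF in ambulatory units over a two-year period before the trial. They say nothing about CSB++, about whether sessions were still held, or about how many families then stayed away.

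**Conclusion.** The gap is real and narrow. Followed as written, definition 3 scores a held consultation missed during a CSB++ shortage as non-adherence and excuses the same miss during a RUTF or RUSF shortage. That is a rule giving inconsistent results, not a missing detail. Definition 3 adherence is therefore not comparable across unit types. The non-adjusted arm contrast could be biased if the share treated at CSB++ sites differs by arm; the adjusted model includes type of unit.

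The conclusion assumes that one MAM platform dispenses CSB++ for treatment, and that some consultations are held during a CSB++ shortage and missed. Size and direction cannot be computed from the documents. No primary outcome is affected.

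**What to change.** In SAP 5.2, definition 3, replace the reference to the two named products with: *a shortage of the product the unit dispenses for that child's treatment (RUTF, RUSF or CSB++)*. Use the same definition in the analyses by type of treatment unit.

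State which record identifies a shortage. Protocol 3.5.3 says the copied register data include inputs given, which may be enough; unit stock records are the alternative. The documents do not show that CSB++ stock status is recorded, so this should be checked before the wording is adopted.

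If CSB++ shortages cannot be identified, report definition 3 only for RUTF and RUSF units and say that it is not comparable across unit types.

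The cost is one phrase in the SAP and a small data check on CSB++ stock status.
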